4.3. PATIENTS FOR THE PHARMACOGENOMIC SUBSTUDY

4.3.1. Inclusion Criteria

1. All patients included in trial PM104-B-003-10 will be eligible.
2. Only those patients who have themselves or their representatives voluntarily signed the Informed Consent Form for the PGx study will participate.

4.3.2. Exclusion Criteria

1. Patients who do not consent to participate in this substudy (by themselves or through their representatives). Refusal to participate in the PGx substudy will not affect participation in the main trial PM104-B-003-10.

5. PLAN OF THE STUDY

5.1. DURATION OF STUDY (WHOLE POPULATION)

The total duration of the study will be approximately 36 months, including about 24 months of active enrollment.

Consenting patients will be followed until death, or until the date of study termination, whichever occurs first.

- Planned start date (first patient on study): 1Q11.
- Planned enrollment period: 24 months.
- Planned study termination will occur:
 - Depending on the development/extension of the trial:
 - Three months after the last treatment visit of the last evaluable patient if the study ends at the first stage.
 - Six months after the last treatment visit of the last evaluable patient, if the study proceeds to the second stage.
 - Or 12 months after the last patient included in the study, if neither of the above have occurred.

5.2. DURATION OF STUDY AND TREATMENT (PER PATIENT)

Patients will receive study treatment as long as it is considered to be in their own benefit (see Section [7.2.3](#)). Patients will be evaluated at scheduled visits in up to three study periods:

- **Pre-treatment:** from the signature of informed consent to the first infusion of Zalyps[®].
- **Treatment:** from the first infusion of Zalyps[®] to the last administration of study drug plus 30 days, or onset of subsequent therapy or death, whichever occurs first. An end-of-treatment visit will be performed within 30 days after last dose administration.
- **Follow-up:** all patients will be followed up after the end of treatment:
 - Patients who discontinue treatment without progression will be followed every three months until disease progression, other antitumor therapy or death or until the date of study termination, whichever occurs first.
 - After disease progression or after other antitumor therapy, patients will be followed every three months until death, or until the date of study termination, whichever occurs first.

Patients may withdraw their consent at any time; no further study activities will be conducted on them.

Patients will be considered to be **on-study** from the signature of the informed consent to the end of follow-up period. Patients will be considered to be **on-treatment** for the duration of their treatment and in the first 30 days following the date of the last study drug administration, or until the onset of subsequent therapy or death, whichever occurs first. **End of treatment** is defined as the day of the last study drug dose administration plus 30 days, or onset date of subsequent therapy or the date of death, whichever occurs first.

5.2.1. Discontinuations

5.2.1.1. Treatment Discontinuation

The end of treatment occurs when an enrolled patient ceases to receive the study medication, regardless of the circumstances. The primary reason for any discontinuation will be recorded on the patient's Case Report Form (CRF). By convention, the date of end of treatment will be the day of the last Zalyps[®] administration plus 30 days, or the date of the onset of subsequent therapy or the date of death, whichever occurs first.

If a patient discontinues treatment, every effort should be made to complete the scheduled assessments.

5.2.1.2. Reasons for Treatment Discontinuation

Administration of the study treatment should be discontinued if this is considered to be in the best interest of the patient. More specifically, treatment will be discontinued due to any of the following reasons:

- Disease progression.
- Unacceptable toxicity (including any toxicity leading to the need for a third dose reduction or severe hypersensitivity reactions, except in the event of obvious clinical benefit, in which case the patient could be allowed to remain on treatment after having discussed and agreed on the case with the Sponsor(s)).
- Patient's representative refusal and/or non compliance with study requirements.

- Intercurrent serious illness.
- Protocol deviation with an effect on the risk/benefit ratio of the clinical trial.
- Treatment delay > 2 weeks or impossibility to administer both Day 8 and Day 15 doses on a given cycle (except in case of clear clinical benefit, with the Sponsor(s)'s approval).
- Requirement of > 2 dose reductions (except in case of clear clinical benefit, with the Sponsor(s)'s approval).
- Administrative reasons or Sponsor(s)'s decision.

Regardless of the reason, patients who discontinue the treatment must not be re-treated at any time.

Any subsequent therapies for the patients may be provided off-study according to the Investigator's criteria.

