5.3. REPLACEMENT OF PATIENTS

Patients must be replaced if they are considered not evaluable for efficacy, i.e., if they are withdrawn from the study due to significant clinical deterioration of unknown reason, hypersensitivity reactions, patient refusal or unrelated AEs without any tumor assessments after the start of study treatment.

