10.1. SAMPLE SIZE

The optimum two-stage design to test the null hypothesis that the overall response rate (ORR) is $\leq 3\%$ versus the alternative that $ORR \geq 20\%$ was selected. After testing the drug on 12 patients in the first stage, the trial will be terminated if there is not any responder. If the trial goes on to the second stage, a total of 29 patients will be studied, 12 from the first stage and 17 from the second stage. If the total number responding is less than or equal to 2 (two patients), the drug will be considered not interesting in the setting of patients treated with this disease and with this schedule. This design has an expected sample size of 17.20 and a probability of early termination of 0.69. If the drug is actually not effective, there is a 0.05 probability of concluding that it is (type I error). If the drug is actually effective, there is a 0.1 probability of concluding that it is not (type II error).

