4.1.1. Efficacy population

To be evaluable for efficacy, eligible patients must have received at least four infusions of the six infusions corresponding to the first two cycles and have at least one disease measurement recorded not less than six weeks after treatment onset.

In addition, any eligible patient who receives at least two of the three infusions in one treatment cycle and develops disease progression or dies due to progressive disease (PD) prior to response evaluation will be considered evaluable for the main endpoint (ORR) and will be categorized as an "early progression".

Patients withdrawn due to toxicity without any tumor assessment after the start of study treatment will be considered as "treatment failures" and will not be replaced.

Patients withdrawn due to significant clinical deterioration of unknown reason, or due to hypersensitivity reactions or unrelated AEs, and patients who refuse to continue on study for any reason without any tumor assessment after the start of study treatment will be considered not evaluable for efficacy and will be replaced.

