10.1.3. Reasons for treatment discontinuation

Table 10.1.3.1 Reasons for treatment discontinuation.

	T	Total		
	N	%		
Progressive disease				
Toxicity (Drug related AE)*				
Death**				
Patient refusal				
Investigator decision				
Other***				

(*) See tables 10.1.3.6; (**) Table 10.1.3.7; (***) Table 10.1.3.5

Table 10.1.3.2 Reasons for treatment discontinuation by number of cycles received.

	Cyc	cle 1	Cyc	cle 2		•••	-	Fotal
	N	%	N	%	N	%	N	%
Progressive disease Patient refusal								

Table 10.1.3.3 Time on treatment (months).

|--|

^(*) Time from first infusion of the study drug to the day of the last study drug administration plus 30 days, or onset of subsequent therapy or death, whichever occurs first.

Table 10.1.3.4 Listings of patients and time on treatment.

Patient ID.	Day of first infusion	Day of last dose administered	Number of cycles received	Time on treatment (months)
				· · · · · · · · · · · · · · · · · · ·

Table 10.1.3.5 Listings of treatment discontinuation other than progressive disease.

Patient ID.	Cycle	Reason	Specify

Table 10.1.3.6 Listing of treatment discontinuation due to adverse events (AEs).

Patient ID.	PT MedDRA Code	Grade		Relationship	Significant
1 attent 1D.	1 1 MedDKA Code	Grauc	•••	Relationship	consequence

Table 10.1.3.7 Listing of treatment discontinuation due to death.

Patient ID. Cycle	Cause of death	Last study drug administration date	Death date	Time from last Study drug administration to death (days)
•				

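### Severe hypersensitivity is unacceptable toxicity in Protocol 5.2.1.2, yet hypersensitivity withdrawals without a tumor assessment are replaced, so drug-caused non-responders can leave the primary ORR denominator

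*Protocol*

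**What the plan says.** Protocol 5.2.1.2 lists the reasons for stopping treatment. One is "Unacceptable toxicity (including any toxicity leading to the need for a third dose reduction or severe hypersensitivity reactions". Two later entries cover "Treatment delay > 2 weeks or impossibility to administer both Day 8 and Day 15 doses on a given cycle" and a need for more than two dose reductions. Neither of these states a cause. Protocol 5.2.1.1 adds: "The primary reason for any discontinuation will be recorded on the patient's Case Report Form (CRF".

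Two evaluability rules then apply to patients with no tumor assessment after treatment start:

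- **Failure rule** (Protocol 8.1 and 10.3.1, SAP 4.1.1, synopsis efficacy evaluations). SAP 4.1.1 begins "Patients withdrawn due to toxicity without any tumor assessment after the start of study treatment will be considered as" and goes on to class these patients as treatment failures who are not replaced.
- **Replacement rule** (the same sections, plus Protocol 5.3 and the synopsis entry on replacement). Protocol 5.3 treats patients as not evaluable, and replaces them, "if they are withdrawn from the study due to significant clinical deterioration of unknown reason, hypersensitivity reactions, patient refusal or unrelated AEs", again where there is no tumor assessment after treatment start.

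For reporting, SAP Table 10.1.3.1 has a row "Toxicity (Drug related AE") next to progression, death, refusal, investigator decision and other. It has no row for delay, missed doses or reductions.

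**The concern.** A patient withdrawn for severe hypersensitivity without a scan meets both rules, and they give opposite results: stay in the ORR denominator as a failure, or leave it and be replaced. The plan states no order of precedence, and the SAP repeats the conflict. Such a patient has not responded, and the drug is the likely cause of the stop. Removing the patient and enrolling another gives the trial a second chance at a response. The futility look (SAP 8.6) and the final decision both count evaluable patients, and the final decision turns on three responders in 29, so a few patients matter.

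The secondary question is how to class a stop under the delay or missed-dose reason when drug toxicity caused it. Protocol 7.2.3 skips a dose when blood counts, liver, renal or albumin values or toxicity grades fail the criteria, so toxicity is an expected cause. No text says whether this is a toxicity withdrawal for the failure rule.

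**Working it through.** **1. The plan's own figures.** Inputs from Protocol 10.1: null rate 3%, alternative 20%, "a total of 29 patients will be studied, 12 from the first stage and 17 from the second stage", stop at 0 of 12, not interesting at 2 or fewer of 29.

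- Early termination under the null: 0.97^12 = 0.694 (stated 0.69).
- Expected sample size: 12 + (1 − 0.6938) × 17 = 17.20 (stated 17.20).
- P(declare active) = Σ over x1 ≥ 1 of P(X1 = x1) × P(X2 ≥ max(3 − x1, 0)), with X1 binomial on 12 and X2 binomial on 17.
- At 3%: 0.2575 × 0.0909 + 0.0438 × 0.4042 + 0.0048 = 0.046 (stated ceiling 0.05).
- At 20%: 0.901 (stated 0.90).

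The design reproduces. The classification conflict does not alter these figures; it alters who is among the 12 and the 29.

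**2. Effect of replacing instead of failing.** Let h be the share of treated patients withdrawn for hypersensitivity with no assessment. The documents give no value, so h is an assumption. All such patients are taken as non-responders, and 3% and 20% as rates among all treated patients. The rate among evaluable patients is then p / (1 − h), and 29 / (1 − h) patients must be treated to obtain 29 evaluable.

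| h (assumed) | Null rate among evaluable | Treated for 29 evaluable | Type I error |
|---|---|---|---|
| 0% | 3.00% | 29.0 | 0.046 |
| 3% | 3.09% | 29.9 | 0.050 |
| 5% | 3.16% | 30.5 | 0.052 |
| 10% | 3.33% | 32.2 | 0.059 |
| 15% | 3.53% | 34.1 | 0.068 |

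If these patients are kept as failures, type I error is 0.046 and power 0.901 whatever h is.

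**3. Effect on the estimate.** With three responders, ORR is 3/29 = 10.3% (exact 95% CI 2.2% to 27.4%). Counting one such patient as a failure on top of the 29 gives 3/30 = 10.0%; counting five gives 3/34 = 8.8%.

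**4. The delay and missed-dose stop.** Take a patient who receives Day 1 of Cycle 1, misses Day 8 and Day 15 because of drug toxicity, stops, and has no scan. One infusion is below the four of six needed for evaluability and below the two of three needed for early progression. Read as a toxicity withdrawal, the patient is a failure. Read as a delay or missed-dose stop, the patient is in neither the failure rule nor the replacement list. The text does not choose.

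**The case against.** The replacement wording is the same in every section that carries it, so it may be a deliberate exception for hypersensitivity that overrides the general toxicity rule. It applies only without an assessment, and Protocol 5.8 asks for a tumor assessment at the end-of-treatment visit whatever the reason for stopping, so few patients should qualify. SAP 7.3 repeats the efficacy analysis in all treated patients, and Table 11.2.1.5 keeps them in its denominator. At an assumed 3% to 5% replaced, type I error is 0.050 to 0.052, close to the nominal 0.05.

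Most of this stands as a limit on size. It does not remove the conflict. Even as a deliberate exception, the rule takes drug-caused non-responders out of the primary denominator. The all-treated analysis repairs neither the futility look nor the final count, which use evaluable patients. Protocol Appendix 3, section 2.9.1, itself warns against resting conclusions on a selected evaluable subset.

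A reader might go further and infer that toxicity discontinuations are filed under non-toxicity reasons and so under-counted. The documents do not support that:

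- Protocol 5.2.1.2 is a list of stopping criteria. It is not given as a CRF code list, and it labels no entry as non-toxicity.
- Its toxicity entry already names the third dose reduction, so the entry on more than two reductions is a duplicate.
- SAP Table 10.1.3.1 has a row for drug-related events, and nothing sends delay stops to another row.
- Protocol 9.2.1 makes a laboratory abnormality that leads to discontinuation an adverse event, and SAP Table 12.2.1.1 separately counts discontinuations associated with drug-related events.
- The phase I median relative dose intensity of 77.9% gives no cause and does not show that toxicity stops were frequent.

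One further gap lies outside this point. A one-infusion patient scanned before six weeks fits no efficacy category under any label, and relabelling would not close it.

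**Conclusion.** The contradiction on hypersensitivity is real and touches the primary endpoint. Applying the replacement rule biases ORR upward whenever a drug-caused hypersensitivity withdrawal has no tumor assessment. The size is unknown because no frequency is given. Under the assumptions shown (replaced patients are non-responders, and the design rates refer to all treated patients), type I error rises from 0.046 to 0.052 at 5% replaced and to 0.059 at 10%. At 3% or less it stays within 0.05.

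The delay and missed-dose reason is a secondary ambiguity. It carries a risk of inconsistent coding under a single primary reason and leaves some early stops without an efficacy class. A downward bias in the toxicity-discontinuation rate is not shown.

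**What to change.** This is classification only; no stopping rule changes.

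1. Reconcile Protocol 5.2.1.2, 5.3, 8.1 and 10.3.1, the synopsis (efficacy evaluations, replacement, and reasons for ending treatment) and SAP 4.1.1, so that a drug-related hypersensitivity withdrawal with no tumor assessment is a treatment failure in the ORR denominator and is not replaced. Changing 5.3 alone would leave the other sections in conflict.
2. State in SAP 4.1.1 that withdrawal due to toxicity is decided by cause and includes delay and missed-dose stops caused by the drug.

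The cost is wording in the protocol, synopsis and SAP, plus a coding instruction. The reported ORR may be slightly lower.

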5.2.1.3. Study Discontinuation

Study discontinuation occurs when an enrolled patient ceases to participate in the study, regardless of the reason. Patients have the right to withdraw consent at any time; if this is the case, no further follow-up should be performed.

The date and reason for study discontinuation will be clearly documented on the patient's CRF.

5.2.2. Protocol Deviations

A protocol deviation is defined as any departure from what is described in the protocol of a clinical trial approved by an Independent Ethics Committee/Institutional Review Board (IEC/IRB) and Competent Authorities. Therefore, this applies to deviations related to patient inclusion and clinical procedures (e.g., assessments to be conducted or parameters to be determined), and also to other procedures described in the protocol that concern the Good Clinical Practice (GCP) guidelines or ethical issues (e.g., issues related to obtaining the patients' Informed Consent, data reporting, the responsibilities of the Investigator, etc.).

Deviations with no effects on the risk/benefit ratio of the clinical trial (such as minimal delays in assessments or visits) will be distinguished from those that might have an effect on this risk/benefit ratio, such as:

- Deviations that might affect the clinical trial objectives, such as those involving the inclusion/exclusion criteria (which could mean that the patient is not eligible for the trial) and those having an effect on patient evaluability.
- Deviations that might affect the patient's well-being and/or safety, such as an incorrect dosing of the investigational medicinal product (IMP, this is Zalypsia®) due to not following dose adjustment specifications or an incorrect preparation of the medication.
- Deviations related to the following of GCP guidelines as described in the protocol and regulations in force, such as deviations when obtaining the Informed Consent or not following the terms established for reporting serious adverse events, etc.

As a general rule, NO deviations that may have an effect on the risk/benefit ratio of the clinical trial will be authorized. All protocol deviations considered particularly relevant according to regulations, which are related to ethical issues, fulfillment of GCP

guidelines and trial procedures, will be notified to the pertinent IEC/IRB and, if pertinent, to the competent authorities as established by local regulations.

5.3. REPLACEMENT OF PATIENTS

Patients must be replaced if they are considered not evaluable for efficacy, i.e., if they are withdrawn from the study due to significant clinical deterioration of unknown reason, hypersensitivity reactions, patient refusal or unrelated AEs without any tumor assessments after the start of study treatment.

5.4. STUDY TERMINATION (CLINICAL CUTOFF)

Study termination will occur:

- Depending on the development/extension of the trial:
 - Three months after the last treatment visit of the last evaluable patient if the study ends during the first stage.
 - Six months after the last treatment visit of the last evaluable patient, if the study proceeds to the second stage.
- Or 12 months after the last patient included in the study, if neither of the above have occurred.

5.5. PRE-TREATMENT EVALUATION

During the pre-treatment period, and once the patient or his/her representative has signed the Informed Consent Form, the Investigator will confirm the patient's eligibility for the study by conducting the following assessments (Table 5).

Additional information on the collection and processing of pharmacodynamic and PGx samples will be provided as a separate document in the “Guide for Identification, Packaging and Shipment of Pharmacodynamic and Pharmacogenomic Samples”.

Table 5. Pre-treatment assessments

	PRE-TREATMENT ASSESSMENT	TIME
1. History and clinical examination	
 Written informed consent. Medical history: 
 Date of diagnosis of the primary disease. Demographic information (race/ethnicity, age). Prior treatments (surgery, radiotherapy, chemotherapy, immunotherapy), specifying the best response and the date of PD. Concomitant diseases and treatments. Weight, height and BSA. Complete physical examination. Vital signs: heart rate, blood pressure and body temperature. ECOG PS (Appendix 1). 	Prior to any specific study procedures. All within four weeks prior to Day 1 of Cycle 1. Complete physical examination, ECOG PS, vital signs, and weight must be repeated on Day 1 of Cycle 1, prior to administration of the first Zalyps [®] infusion.
	
 ECG* LVEF* by ECHO. 	Within four weeks prior to Day 1 of Cycle 1; ECG must be repeated on Day 1 of Cycle 1, before the administration of the first Zalyps [®] infusion.
2. Laboratory tests	
 Hematology: differential WBC (neutrophils, lymphocytes), hemoglobin and platelets. Biochemistry A: liver function tests (ALT, AP, AST, LDH, total bilirubin), creatinine, CPK, troponin I*, glucose, and serum electrolytes (Na⁺, Cl⁻, K⁺, Ca⁺⁺, Mg⁺⁺). Biochemistry B: total protein and albumin. 	All within one week prior to Day 1 of Cycle 1. Repeat Hematology and Biochemistry A on Day 1 of Cycle 1 prior to treatment with Zalyps [®] (a window of -2 days allowed), if the treatment is administered more than one week after the pre-treatment test. Repeat Biochemistry B on Day 1 of Cycle 1 whenever clinically indicated.
3. Calculated creatinine clearance	Calculated according to Cockcroft and Gault's formula (Appendix 4).	Within one week prior to Day 1 of Cycle 1. Repeat on Day 1 of Cycle 1 whenever clinically indicated.
4. Pregnancy test, if applicable		Within two weeks prior to registration and repeat on Day 1 of Cycle 1.
5. Tumor assessment	CT-scan or MRI of all measurable/evaluable sites of disease, as per RECIST v. 1.1. Documentation of PD is mandatory.	Within four weeks prior to the first dose of Zalyps [®] .
6. PK samples	See Section 6 .	Blood samples will be collected on Day 1 of Cycle 1: one before Zalyps [®] infusion, and one 5 min before the end of infusion.
7. Pharmacodynamic and pharmacogenomic samples, from consenting patients	See Section 8.4 and 8.5.	CTCs will be collected on Day 1 of Cycle 1 before Zalyps [®] infusion. Paraffin-embedded tumor tissue (obtained at diagnosis of the tumor) can be collected any time after registration.
8. Other tests	When indicated by the clinical and laboratory context.	Within four weeks prior to Day 1 of Cycle 1.

* All troponin I determinations, ECGs and LVEFs will be reviewed by external cardiologists.

ALT, alanine aminotransferase; AP, alkaline phosphatase; AST, aspartate aminotransferase; BSA, body surface area; CPK, creatine phosphokinase; CT, computed tomography; CTCs, circulating tumor cell(s); ECG, electrocardiogram; ECHO, echocardiography; ECOG, Eastern Cooperative Oncology Group; LDH, lactate dehydrogenase; LVEF, left ventricular ejection fraction; MRI, magnetic resonance imaging; PD, progressive disease; PK, pharmacokinetics; PS, performance status; RECIST, Response Evaluation Criteria In Solid Tumors; WBC, white blood cells.

